#### **2. ABSTRACT (Summary):**

Sleeve gastrectomy is now the most commonly performed bariatric surgery. While many studies have evaluated factors that may minimize post-operative hemorrhage and staple-line leak, we are unaware of any studies that compare outcomes between devices from the two main stapler manufacturers used in this surgery, Covidien and Ethicon. The purpose of this study is to compare intraoperative characteristics, such as time to create sleeve, intraoperative bleeding, and time needed to load each cartridge, and post-operative characteristics, such as any complication requiring readmission (leak or hemorrhage), further surgical intervention, and weight loss, between patients who underwent sleeve

gastrectomy with Covidien devices and Ethicon devices. Since we typically use the Ethicon device more frequently for this surgery due to cost, we want to test if one device is superior to another in clinical outcomes and use cost as a secondary metric. If one device has better clinical outcomes, it will be the preferred device regardless of cost. If neither proves superiority, we can justify using cost to determine which device to use in patient care.

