## **2.4 Methodology / Technical Approach (including the number of subjects/records to be studied):**

New bariatric patients who have elected for a sleeve gastrectomy as part of standard of care will be invited to participate in the study during the bariatric clinic at William Beaumont Army Medical Center. Patients who meet the inclusion criteria will be invited to participate in the study. Please see Section 6.2.3 for specific details on study recruitment and Section 6.2.4 for specific details on the consent process. These patients will be consented in the bariatric clinic by a research resident listed on the protocol.

Three folders will be made, one for each bariatric surgeon, and 25 Covidien cards and 25 Ethicon cards will be placed into each for a total of 150 patients. All bariatric surgeons are trained and familiar with both devices. Once consented, a card will be removed at random to determine which stapler will be used. Bioabsorbable staple line reinforcement will be utilized with both staplers. Once in the operating room, the case start time, time from first staple firing to completion of sleeve, total stapler loads required, number of staple misfires, character of any staple line bleeding, and time for tech to load each cartridge will be recorded on a data collection sheet by a research resident, listed as an associative investigator on this protocol. The subject's post-operative course will follow the bariatric protocol. During follow-up, they will be monitored for weight loss, post-operative complications, and any other required interventions. This information will be obtained by reviewing the subject's medical record after follow-up appointments. Per the bariatric protocol, subjects will follow-up as noted in 6.3.5. If a patient withdraws consent for the study prior to surgery, they will still receive surgery and perioperative treatment in line with institutional protocol, and they will be withdrawn and create a vacancy for a new subject. If a patient withdraws consent after surgery, we will cease logging data for the study on that subject. We will clarify whether they want all data to be removed from the study or if they simply want no more data to be entered into the study and abide by their wishes, and they will remain in the original randomized group in accordance with intention-to-treat principles.

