**5. BACKGROUND AND SIGNIFICANCE SECTION**

**5.1 Literature Review and Preliminary Data and/or Findings:**

Demonstrate that you have done a comprehensive literature search that includes the following:

**a. Date of Search:** 02 Sept 2015

**b. Search terms used:** Laparoscopic sleeve gastrectomy, stapler, bariatric surgery, Covidien, Ethicon

**c. Databases Searched:** PubMed, Google Scholar

In 2011 and 2012, it was found that 34.9% of Americans were obese . As a result, many patients will turn to bariatric surgery to assist with weight loss and resolution of obesity-related comorbidities. The three most commonly utilized bariatric procedures are the roux-en-y gastric bypass (RYGB), adjustable gastric band placement, and sleeve gastrectomy. While the RYGB was historically the most commonly performed procedure, laparoscopic sleeve gastrectomy is rapidly gaining popularity, accounting for 0.9% of bariatric procedures in academic centers in 2008 to 36.3% in 2012 . According to the American Society for Metabolic and Bariatric Surgery (ASMB), laparoscopic sleeve gastrectomy is now the most commonly performed bariatric surgery in the United States as of 2013 .

Sleeve gastrectomy was first described as part of a biliopancreatic diversion with duodenal switch in 1998 and was performed laparoscopically in 1999. It was first done as a stand-alone procedure in 2003 as part of a two-stage weight loss procedure and was recognized by the ASMBS as an acceptable option for primary bariatric surgery in 2009. The procedure is most commonly performed using a linear cutting stapler to form the gastric sleeve. The most concerning complications from this procedure include staple-line leak and hemorrhage, which occur in 2.8 and 3% of patients overall, respectively. Multiple studies have been conducted to determine how to reduce complication using staple line analogs, such as oversewing with suture, using bovine pericardium, applying liquid hemostatic matrices, and using an absorbable polymer membrane (GORE SEAMGUARD Reinforcement, W. L. Gore & Associates, Elkton, MD). In a recent study, the absorbable polymer membrane was found to have lowest leak and overall complication rate.

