**6.3.2 Study Methodology/Procedures:**

Patients who express an interest in bariatric surgery will attend a bariatric seminar and initiate the process of scheduling bariatric surgery per department protocol. Once qualified for surgery, the patients will present to bariatric clinic, which takes place in the general surgery clinic on Tuesdays, and have a one-on-one discussion about their desired surgery with a staff physician. If the patient desires a sleeve gastrectomy, the study will be discussed. Consent will be obtained, and the patient will be randomized into the Covidien or Ethicon group. The subject will proceed with surgery per department protocol. In the operating room, a data collection sheet will be available in the operating room to make note of time for creation of sleeve from first firing to completion, total number of staple loads fired, number of misfires, character of any bleeding at the staple line and which interventions were required to control it, and time it takes for the surgical technologist to reload the stapler. At William Beaumont surgical technologists are trained on loading each linear cutting stapler by the Covidien and Ethicon representatives. We will still ensure at the start of the case they are familiar with loading the provided device. No additional training for device will be mandated, as surgical technologist turnover would make this difficult to provide equal training, and it would detract from internal and external validity, since we do not normally provide extra training. Typically the sleeve is created by staff or higher level residents (PGY-2 and above). However, all residents are trained on the devices and are therefore capable of creating the sleeve with close staff supervision, as is standard for our institution. For the purpose of this study, we intend on maintaining this practice since all level residents may be assisting and performing this surgery throughout their residency and deviation would lead to questionable internal validity. After surgery, patients will be admitted to the hospital, and care will follow the department's bariatric protocol. Once discharged, they will follow-up at 3 weeks, 6 weeks, 3 months, 6

months, and then annually. Subjects will be followed for 1 year after surgery. During that time, weight loss, presence of staple line leaks, any readmissions, and any other interventions will be monitored.

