#### **6.4.2 Data analysis:**

For the continuous primary endpoints, the two-sample t-test for 2 means will be used to compare the 2 Devices at Surgery. For the continuous secondary endpoints, such as weight loss, the General Linear Mixed Model Analysis for repeated measures over time will be used to test for the Device effect, Time effect and the Device by Time Interaction. For the binary secondary endpoints (Yes/No), such as Staple line leak, Readmission or ER visits, further sleeve interventions, over time, the General Estimating Equations (GEE) analyses will be used to test for Device effect, Time effect and the Device by Time Interaction. For all tests, the level of significance is set at 0.05.

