#### **6.4.3 Sample Size Estimation:**

75 in each arm for a total of 150 patients. The preliminary power analysis indicated 64 in each arm to be sufficient, to be able to detect a medium effect size of 0.5 for the two-sided t-test, with  $\alpha = 0.05$  and 80% power, so 11 extra patients per arm have been added for attrition. The power analysis was based on the research hypothesis of a difference in the 2 devices, with this superiority study using time to create sleeve as the primary variable.

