### 6.5.2 Expected Adverse Events from Research Risks and Reporting:

Overall, the risk of complications from sleeve gastrectomy generally falls in the less likely range (1%-5%). According to other studies that have been performed using both staplers, they did not report significant differences in staple line leaks. Additional risks as a result of this study are expected to fall in the rare but serious range (<1%). Such risks may include minor staple line bleeding which will be addressed in the operating room, which may be attributed to a surgeon using one stapling device less than another despite being fully trained for both. Post-operative staple-line leak, pain, dehydration, infection, and blood clots are also known complications of the surgery, but the study is not expected to alter the likelihood of these events.

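### With about four leaks expected, the planned GEE for staple line leak cannot support its Device-by-Time test, and its Device result depends on an unstated choice of test

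*Combined protocol and SAP*

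**What the plan says.** Section 6.4.2 names staple line leak, readmission or ER visits, and further sleeve interventions as binary secondary endpoints followed over time. For these, "the General Estimating Equations (GEE) analyses will be used to test for Device effect, Time effect and the Device by Time Interaction". It adds: "For all tests, the level of significance is set at 0.05". It does not say:

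- whether visit is categorical or linear;
- whether a leak counts only at the visit where it occurs or at every visit from then on;
- which standard error is used, or whether the test is Wald or score;
- what happens if events are few.

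No other section fills these gaps.

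The figures needed to judge the plan are in the protocol. Section 5.1 cites "staple-line leak and hemorrhage, which occur in 2.8 and 3% of patients overall, respectively". Section 6.5.2 places complications in general between 1% and 5%. Section 6.4.3 plans 75 per arm, from 64 needed for sleeve creation time, "so 11 extra patients per arm have been added for attrition". Section 6.3.2 states "Subjects will be followed for 1 year after surgery". The table in 6.3.5 shows six post-operative adverse-event assessments (day 1, weeks 3 and 6, months 3 and 6, year 1).

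**The concern.** A repeated-measures logistic model with an interaction needs events spread over both arms and over the visits. About four leaks in the whole trial cannot provide that. Two problems follow. The Device-by-Time test asks for contrasts between cells that mostly hold no event. The Device test can meet an arm with no leak at all; the estimated log-odds ratio then runs off towards infinity, and the p-value reflects the choice of standard error rather than the data.

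Leak is a secondary outcome, but it is not a minor one for the decision. The abstract lists it among the outcomes to be compared and says "If one device has better clinical outcomes, it will be the preferred device regardless of cost". A chance split of 0 v 1 or 0 v 2 leaks could be reported as a significant leak difference under one permissible reading of 6.4.2, and as nothing at all under another.

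**Working it through.** **Inputs.** 75 per arm (6.4.3), leak rate 2.8% (5.1), range 1% to 5% (6.5.2), alpha 0.05 (6.4.2), six assessments (6.3.5). The plan's own sample size reproduces: for effect size 0.5 and two-sided 0.05, the noncentral t gives 79.5% power at 63 per arm and 80.1% at 64; 64 + 11 = 75. That figure concerns sleeve creation time, not leak.

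**Expected leaks.** 75 x 0.028 = 2.1 per arm, 4.2 in total; 2 x 64 x 0.028 = 3.6 if 64 per arm are analysed.

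**Device by Time, categorical visit.** Assume leaks are spread evenly over visits.

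- Leak coded at its own visit: expected empty cells = 12 x (1 - 0.028/6)^75 = 8.4 of 12. With only the five visits after discharge, 10 x (1 - 0.028/5)^75 = 6.6 of 10. The interaction is not estimable.
- Leak coded cumulatively: by simulation, every cell is non-empty in about 9% to 52% of trials, depending on the assumed timing. The full test also needs a new leak at every later visit, otherwise adjacent visits are identical. Both conditions hold in only about 0.03% to 1.2% of trials.

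**Device by Time, linear visit.** With leaks coded at their own visit, both arm slopes are finite in only 58% to 61% of simulated null trials. Among those, a robust Wald interaction test rejects in 20% to 28%. One cause is that an arm with a single leak at an interior visit gets a slope standard error near zero (0.0004 to 0.0016).

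**Device, Device-only fit, exact enumeration over both arms' leak counts, no true difference.**

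- Chance that a given arm has no leak: 0.972^75 = 0.119. Chance that exactly one arm has none: 2 x 0.119 x 0.881 = 0.209.
- Robust variance of an arm's log-odds with r = leaks/n over six visits: (1 - r)/(n r (1 - r/6)^2). An arm with no leak adds only about 1/n = 1/75 = 0.013 while its log-odds diverges, so the Wald test rejects whenever exactly one arm is empty.
- Generalized score statistic for a v b leaks, m = a + b: (a - b)^2 / (m(1 - m/150)).

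| Per arm, leak rate | Robust Wald | Score | Fisher |
|---|---|---|---|
| 75, 2.8% | 21.0% | 4.1% | 0.5% |
| 64, 2.8% | 27.2% | 3.6% | 0.3% |
| 75, 1% | 49.8% | 0.7% | 0.01% |
| 75, 5% | 5.2% | 4.9% | 1.5% |

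A model-based Wald test rejects in under 0.1% at 75 per arm and 2.8%. Of the 21.0 points for robust Wald, 6.1 come from 0 v 1 and 6.5 from 0 v 2, together 12.6/21.0 = 60%. Only 0.08 points come from trials with leaks in both arms.

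**Example, 0 v 2.** A GEE fit in statsmodels reports convergence with log-odds 23.15 (the value depends on where iteration stops).

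- Robust: r = 2/75 gives variance 0.9733/(2 x 0.9956^2) = 0.491, SE 0.70, z = 23.15/0.70 = 33, p < 0.0001.
- Model-based: SE about 75,000, p > 0.99.
- Score: 4/(2 x (1 - 2/150)) = 2.03, p = 0.15.
- Fisher: p = 0.50.

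**Planned model.** With Device, linear Time and their interaction (independence working correlation, robust SE, about 1,200 null trials per coding), the Device Wald test rejects in 18% (visit centred), 23% (months), 28% (visit numbered 0 to 5) and 29% (visit numbered 1 to 6).

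**The case against.** The strongest reply is that 6.4.2 never says robust Wald. A reader might infer that the plan has a 21% false-positive rate for leak. The documents do not support that: the score test is equally consistent with the text and keeps the error near 4%. The 21% is one branch of an unspecified analysis, for a Device-only fit, at a literature rate for patients overall. It is close to nominal at 5%, and 5.1 itself reports the lowest leak rates with absorbable reinforcement, which both arms use. A lower rate makes the robust Wald branch worse, however.

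A second reply is that nobody would publish a log-odds of 23 from a 0 v 2 split. Perhaps so, but the fit reports convergence, and choosing a substitute test after seeing the split is a data-driven choice that the plan could avoid.

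A third is that empty cells depend on leak coding. This is right for the count of 8.4; under cumulative coding the interaction test fails in most trials for a different reason.

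Three further inferences go too far. The primary comparison is a t-test on sleeve creation time and is untouched. The early-stopping rule in 6.4.4 names no test, so it cannot be said that this GEE would trigger it. And the documents give no expected rate for readmission/ER visits or further interventions, so the finding cannot be extended to them without a count.

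**Conclusion.** The concern holds for staple line leak. About four expected leaks cannot support the Device-by-Time test in 6.4.2: it is not estimable with categorical visits and leaks coded at occurrence, and degenerate in nearly all trials with cumulative coding. The Device test is under-specified in a way that matters. At 75 per arm and 2.8%, its null rejection rate is about 21% (robust Wald, Device-only; 18% to 29% in the full model with linear time), about 4% (generalized score) or under 0.1% (model-based Wald). For robust Wald the range over leak rates of 1% to 5% is about 50% to 5%. Nearly all the excess comes from trials in which one arm has no leak. These figures assume equal true rates, at most one leak per patient and complete follow-up; the cell counts and full-model simulations also assume an even spread of leaks over visits. It should be fixed, but it concerns a secondary outcome; the primary analysis and the sample size stand.

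**What to change.** Amend 6.4.2 as follows.

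1. For leak, and for any binary secondary outcome with fewer than a pre-stated total number of events (for example 10, counted with both arms pooled so that the choice does not depend on the split), drop the Device-by-Time test. Readmission/ER visits can keep the planned GEE if they reach the threshold.
2. For leak, compare devices on one variable per patient: any post-operative leak to 1 year. Report separately, by arm, intra-operative leaks found and repaired at the leak test, which the data sheet in 6.3.4 already records.
3. Use Fisher's exact test with the risk difference and an exact 95% confidence interval. If GEE is kept for these outcomes, specify a generalized score test.
4. Describe leak timing without a test.
5. Include all randomised and operated patients, and count a leak at any available visit. Report incomplete follow-up by arm and, separately, patients whose data were removed at their request, since 2.4 allows this ("We will clarify whether they want all data to be removed from the study").

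The cost is wording, plus recording each patient's last follow-up visit from the chart review already planned. There are real downsides. Leak timing gets no formal test, and a leak after loss to follow-up is missed. Fisher's test is conservative: type I error is about 0.5%, and 0 v 6 is the smallest significant split against zero (0 v 4 for the score test). For 2.8% v 5.6%, power is 4.7% with Fisher and 12.6% with the score test. The leak comparison is therefore essentially descriptive, and the plan should say so.

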**3. OBJECTIVES AND SPECIFIC AIMS:**

Primary objectives: Determine if using different brand staplers affects:

1. Time of creation of sleeve from first firing to completion
2. The percent of firings with technical difficulties
3. The time for tech to load each staple cartridge (aware of Hawthorne effect. Since both arms will be subject to Hawthorne effect, the only variable should be the stapler)

Secondary objectives: Determine if using different brand staplers affects:

1. Any bleeding after creation of the sleeve (annotating whether single or multiple interventions are required)
2. Weight loss
3. Leak rates
4. Hospital readmissions or emergency room visits (For complications including but not limited to dehydration, hemorrhage, leak, internal hernia, and pain; will annotate what complication warranted readmission)
5. Further sleeve interventions

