There are two main manufacturers of laparoscopic linear cutting staplers that are Food and Drug Administration-approved for use in laparoscopic sleeve gastrectomies, and both have options for absorbable polymer membrane reinforcement. These companies are the Covidien with iDrive™ Ultra Powered Stapling System and Endo GIA™ Reinforced Reload with Tri-Staple™ Technology (Covidien, Dublin, Ireland) and Ethicon with the Echelon™ Stapler (Echelon Flex™ Powered Endopath® Stapler; Ethicon Endo-Surgery Inc., Cincinnati, OH, USA), which is compatible with GORE SEAMGUARD for reinforcement. While a study with 26 patients incidentally found no difference in outcomes between the two devices without an absorbable polymer membrane, to our knowledge there is no non-industry-funded study designed to compare intra-operative findings and outcomes in sleeve gastrectomy between the two devices with absorbable polymer membranes. We hypothesize that the sleeve creation time and time needed to load each staple cartridge will be different between the two devices

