### 6.3.5 Study Time Line (*provide diagram or table that outlines sequence/timing of study procedures*):

Assessment	Visit/follow-up interval relative to surgery								
	>1 month pre-op	<1 month pre-op	Day of surgery	Post-op day 1	Post-op week 3	Post-op week 6	Post-op month 3	Post-op month 6	Post-op year 1
Height/Weight	X	X	X	X	X	X	X	X	X
Pre-op bariatric work-up (counseling, labs, endoscopy, ultrasound, psychiatric evaluation)		X							
History and physical			X						
Schedule surgery			X						
Consent/Counseling on study			X						
Randomization			X						
Deidentification and population of secure data sheet			X	X	X	X	X	X	X
Pre-op labs (CBC, pregnancy test, renal panel, type and screen)			X						
Measure time for sleeve creation (sec)				X					
Measure total stapler loads fired				X					
Measure number of loads fired with technical difficulties				X					
Record staple line bleeding and hemostatic interventions				X					
Record time to load each staple cartridge				X					
Labs	X	X		X				X	X
Assess for adverse events				X	X	X	X	X	X

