### 6.3.7 Has any other Scientific Review Committee/Organization reviewed this project for scientific merit? Yes [ ] No [x]. If yes, name the organization, year, and merit/score:

#### 6.4 Statistical Consideration.

##### 6.4.1 Statistical hypothesis, primary endpoints (i.e., primary outcome variables), and secondary endpoints, if any:

Research Hypothesis: As a superiority study, the research hypothesis is Ethicon linear cutting staplers with staple line reinforcement will have different outcomes when performing laparoscopic sleeve gastrectomy when compared to Covidien staplers with staple line reinforcement.

Primary objectives: Determine if using different brand staplers affects:

1. Time of creation of sleeve from first firing to completion
2. The percent of firings with technical difficulties
3. The time for tech to load each staple cartridge (aware of Hawthorne effect. Since both arms will be subject to Hawthorne effect, the only variable should be the stapler)

Secondary objectives: Determine if using different brand staplers affects:

1. Any bleeding after creation of the sleeve (annotating whether single or multiple interventions are required)
2. Weight loss
3. Leak rates

4. Hospital readmissions or emergency room visits (For complications including but not limited to dehydration, hemorrhage, leak, internal hernia, and pain; will annotate what complication warranted readmission)
5. Further sleeve interventions

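### Three primary endpoints are each tested at 0.05 with no success rule, while the trial is sized on one; if any one result counts, the false-positive risk is about 10% to 14%

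*Combined protocol and SAP*

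**What the plan says.** Section 3, repeated in Section 6.4.1, opens "Primary objectives: Determine if using different brand staplers affects" and lists three items: sleeve creation time from first firing to completion, percent of firings with technical difficulties, and the technologist's time to load each cartridge. Neither section ranks them.

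The formal hypothesis in Section 6.4.1 is that Ethicon staplers "will have different outcomes when performing laparoscopic sleeve gastrectomy when compared to Covidien staplers with staple line reinforcement". It names no endpoint. Section 5.1 is narrower and names two of the three: "We hypothesize that the sleeve creation time and time needed to load each staple cartridge will be different between the two devices".

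Section 6.4.2 assigns a two-sample t-test to the continuous primary endpoints, in the plural, and closes: "For all tests, the level of significance is set at 0.05".

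Section 6.4.3 plans 64 per arm for a standardised difference of 0.5, two-sided 0.05 and 80% power, raised to 75 per arm for attrition, "with this superiority study using time to create sleeve as the primary variable". That is the only place where one endpoint is singled out.

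The abstract (Section 2) draws one overall conclusion: "If one device has better clinical outcomes, it will be the preferred device regardless of cost", and "If neither proves superiority, we can justify using cost to determine which device to use in patient care". It does not say which endpoint or endpoints decide this.

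**The concern.** The plan has three primary endpoints in its objectives, two in its background hypothesis and one in its sample size, and nothing reconciles them. It contains no success rule, testing order, all-must-succeed requirement or multiplicity adjustment. Because the hypothesis is so general, a difference on any one endpoint could be said to confirm it.

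The plan does not state that any-one-of-three rule, but it permits it, and the choice could be made after the results are known. The results are meant to decide which stapler is used and whether cost may settle the matter. A verdict resting on the best of three tests would carry a larger false-positive risk than the 5% a reader would assume.

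**Working it through.** **Inputs from the documents.** Three primary endpoints (Sections 3 and 6.4.1); 0.05 per test with no adjustment (6.4.2); standardised difference d = 0.5, two-sided, 80% power, 64 evaluable and 75 enrolled per arm (6.4.3).

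**Assumptions.** All three null hypotheses are true; any one significant result counts as success; each patient contributes one value per endpoint; each test has an exact 5% size. The documents give no correlations, so a range is shown. Reloading between firings falls inside sleeve creation time, so some correlation is likely.

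**Step 1: reproduce the sample size.** The noncentral t calculation for d = 0.5, two-sided 0.05 and 80% power gives 63.77, rounded up to 64 per arm. With the 11 extra patients, 64 + 11 = 75. The plan's figures reproduce. Sleeve-time power at 0.05 is 80.1% with 64 per arm and 86.0% with 75.

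**Step 2: any-one-of-three error, independent endpoints.** 1 − (1 − 0.05)³ = 1 − 0.8574 = 14.3%. The upper bound under any dependence is 3 × 0.05 = 15%.

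**Step 3: the same with a common pairwise correlation ρ.** For normal test statistics,

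error = 1 − ∫ [Φ((1.96 − √ρ·z)/√(1−ρ)) − Φ((−1.96 − √ρ·z)/√(1−ρ))]³ φ(z) dz

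| Assumed ρ | Any-one-of-three error |
|---|---|
| 0 | 14.3% |
| 0.3 | 13.6% |
| 0.5 | 12.5% |
| 0.7 | 10.9% |
| 0.8 | 9.8% |
| 0.9 | 8.4% |

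**Step 4: other decision rules.** If sleeve time alone decides, the error is 5%. If all three must be significant, it is at most 5%. If either of the two endpoints named in Section 5.1 counts, it is 1 − 0.95² = 9.75% when they are independent.

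**Step 5: what the remedies do to power** (simulated two-sample t-tests, 200,000 trials per scenario, ρ = 0, 0.5 and 0.8).

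- *Fixed order, sleeve time then load time, both truly differing by d = 0.5.* Chance of a confirmatory load-time claim: 64.2%, 69.1% and 73.1% at 64 per arm; 74.0%, 77.3% and 80.5% at 75. The ρ = 0 values agree with 0.801² = 64.2% and 0.860² = 74.0%. Sleeve-time power is unchanged.
- *Holm over three.* Sleeve-time power, as the range over ρ:

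| Truly differing by d = 0.5 | 64 per arm | 75 per arm |
|---|---|---|
| Sleeve time only | 65.5% to 66.0% | 73.9% to 74.1% |
| Sleeve and load time | 68.6% to 69.4% | 76.3% to 77.5% |
| All three | 72.2% to 75.0% | 80.0% to 82.7% |

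With all nulls true, the Holm error at 64 per arm is 4.9%, 4.5% and 3.6% at ρ = 0, 0.5 and 0.8.

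**The case against.** The strongest reply is that Section 6.4.3 already calls sleeve creation time the primary variable and ties the power analysis to the research hypothesis. It is also listed first in the objectives. Read that way, its error is 5% and what remains is inconsistent labelling. This stands in part: the intention can be inferred. But the label is not carried into the objectives or the analysis section, and nowhere does the plan say that sleeve time alone determines success.

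Second, three questions may be answered separately, each at 5%, particularly in a study not intended for a marketing submission (Section 6.4.5). That is a defensible convention. The difficulty is the abstract's single verdict, for which no deciding endpoint is named. That verdict could even rest on outcomes listed as secondary, in which case the three-test calculation would not describe its error. This strengthens the need to state the rule and limits what the calculation shows.

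Third, 10% is not a lower bound. It corresponds to an assumed common correlation of about 0.8, and the argument about reloading supports correlation between two endpoints, not all three equally. This is correct. At 0.9 the error is 8.4%, still above 5%.

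Fourth, the t-test on percent of firings with difficulties may be conservative if difficulties are very rare. Assuming six firings per patient, its simulated size is about 5% at difficulty rates of 1% or more per firing and falls to about 1% only near 0.2%. Even then, with independent endpoints, the error is 1 − 0.95² × 0.99 = 10.7%.

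Finally, making load time secondary fits poorly with Section 5.1, and one sentence stating the decision rule might be enough. The fixed order partly answers this by testing load time second. It is also fair that 75 per arm may be the more realistic figure for power, because these outcomes are measured at surgery and Section 2.4 replaces patients who withdraw beforehand.

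**Conclusion.** The concern holds as a conditional statement. If a significant result on any one of the three primary endpoints is taken to confirm the hypothesis, the false-positive risk is about 10% to 14% for common correlations from about 0.8 down to 0, under the assumptions above. Stronger correlation would take it lower, towards 5%. If sleeve creation time is the sole primary endpoint, the risk is 5%. The plan does not choose between these rules.

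The sample size is correct for one endpoint, and sleeve-time power under the plan as written is not reduced. This should be fixed before the results are seen, but it does not undermine the design.

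**What to change.** **Main change.** In Sections 3, 6.4.1 and 6.4.2, name sleeve creation time as the single primary endpoint at two-sided 0.05, as Section 6.4.3 already assumes. Make load time and percent of firings with technical difficulties secondary, reported with estimates and 95% confidence intervals. If confirmatory claims on these are wanted, test them only after a significant sleeve-time result and in a pre-stated order, each step only if the one before it is significant; load time could come first, given Section 5.1.

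Define one value per patient and name the test for each, for example mean load time over the patient's cartridges, and loads with difficulties divided by loads fired. State in Section 2 which endpoint or endpoints decide device preference.

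**Cost.** Wording in Sections 2, 3, 6.4.1 and 6.4.2. No new data are needed: the Section 6.3.5 schedule already covers loads fired, loads with difficulties and "Record time to load each staple cartridge". Sample size and sleeve-time power do not change. The downside is that a null sleeve-time result leaves no confirmatory claim on the other two. If sleeve and load time both differ by d = 0.5, the chance of confirming load time is about 64% to 73% at 64 per arm, or 74% to 80% at 75.

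**Alternative.** Keep all three as primary and state a Holm adjustment. This holds the error at or below 5% but lowers sleeve-time power from 80.1% to about 66% to 75% at 64 per arm, and from 86.0% to about 74% to 83% at 75, depending on how many endpoints truly differ.
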